6.4. Study Intervention Compliance

At each clinic visit, participants will be asked to return any remaining study drug from the previous dosing cycle as well as all used and unused study drug containers.

Treatment compliance will be defined as the number of tablets taken divided by the expected number of tablets and reported as percentage. In case of dose reductions, the expected number of tablets will reflect the new dose level. Tablets that are not returned will be considered to have been taken, unless otherwise specified in the eCRF.

The investigator or designated study site personnel will be responsible for providing additional instruction to any participant who is not compliant with taking the study drug. In the absence of toxicity, if the dosing compliance is not 100%, then investigators or designated study site personnel should re-instruct participants regarding proper dosing procedures and the participant may continue study treatment.

The study site must maintain accurate records demonstrating dates and amount of study drug received, to whom dispensed (participant-by-participant accounting), and accounts of any study drug accidentally or deliberately destroyed. At the end of the study, reconciliation must be made between the amount of study drug supplied, dispensed, and subsequently destroyed or returned to sponsor or its representative.

6.5. Concomitant Therapy

Prestudy therapies administered up to 35 days before first dose of study intervention must be recorded at screening.

Concomitant therapies must be recorded throughout the study beginning with start of the first dose of study intervention to 30 days after the last dose of study intervention.

All therapies (prescription or over the counter medications, including vaccines, vitamins, herbal supplements; non-pharmacologic therapies such as electrical stimulation, acupuncture, special diets, exercise regimens) different from the study intervention must be recorded in the eCRF. Recorded information will include a description of the type of therapy, duration of use, dosing regimen, route of administration, and indication. Modification of an effective preexisting therapy should not be made for the explicit purpose of entering a participant into the study.

Continuous treatment with a GnRHa or surgical castration is mandatory. The choice of GnRHa is at the discretion of the investigator. Dose and dose schedule (without interruption) will be consistent with the prescribing information and will only be adjusted if clinically indicated to maintain castrate concentrations of testosterone.

Salvage radiation for loco-regional pelvic disease and surgical procedures (eg, transurethral resection of the prostate [TURP], urethral and ureteral stent placement) to treat localized progression or symptoms are allowed. Participants receiving these therapies may continue on study drug.

6.5.1. Suggested Therapy

Fracture, fall and hypothyroidism are known risks associated with apalutamide. Participants will be evaluated for fracture and fall risk. Monitor and manage participants at risk for fractures according to established treatment guidelines and consider use of bone targeted agents. Participants are strongly encouraged to obtain an adequate intake of dietary calcium (at least 1,000 mg per day, including supplements if necessary) and vitamin D [at least 800-1,000 international units (or according to the product label-prescribing information in the country of residence) per day for adults 50 years of age and older] and to engage in regular exercise to maintain muscle strength and bone density.

CONFIDENTIAL – FOIA Exemptions Apply in U.S.

Thyroid replacement therapy, when clinically indicated, will be initiated or dose-adjusted.

6.5.2. Prohibited Therapy

Concurrent enrollment in another investigational drug or device study is prohibited during the Treatment Phase.

As a class effect, AR antagonists have been associated with seizures due to an off-target mechanism of action (gamma amino butyric acid chloride channel inhibition). Drugs known to lower the seizure threshold or cause seizures are prohibited and a representative list is included below:

- Atypical antipsychotics (eg, clozapine, olanzapine, risperidone, ziprasidone)
- Bupropion
- Lithium
- Meperidine (pethidine)
- Phenothiazine antipsychotics (eg, chlorpromazine, mesoridazine, thioridazine)
- Tricyclic antidepressants (eg, amitriptyline, desipramine, doxepin, imipramine, maprotiline, mirtazapine)
- Aminophylline/theophylline.

The following medications are prohibited while on study until the End-of-Treatment Visit or 30 days after last dose of study drug. The sponsor must be notified in advance (or as soon as possible thereafter) of any instances in which prohibited therapies are administered. Chemotherapeutic, biologic, or other agents with anti-tumor effect against PC.

- Anti-androgens (except as prescribed in the protocol)
- 5-α reductase inhibitors
- Estrogens
- Progestational agents (eg, cyproterone acetate)
- Androgens
- Oral ketoconazole
- Spironolactone
- Bone targeted agents indicated for the treatment of metastatic PC (bisphosphonates or denosumab) are prohibited (NOTE: bone targeted agents indicated for osteoporosis are allowed).

The sponsor must be notified in advance (or as soon as possible thereafter) of any instances in which prohibited therapies are administered.

6.5.3. Restricted Concomitant Therapy

Highlights of drug interaction with apalutamide are summarized below. Refer to Sections 4.3.4 and 5.10 of the IB and associated addenda for complete details on the drug interaction potential of apalutamide, which include examples of medication that 1) may influence the effect of apalutamide, and 2) their effects may be influenced by apalutamide.

- Medications that inhibit CYP2C8 or CYP3A4: Co-administration of a strong CYP2C8 or CYP3A4 inhibitor is predicted to increase the steady-state exposure of the active moieties (sum of unbound apalutamide plus the potency-adjusted unbound N-desmethyl apalutamide). No initial dose adjustment is necessary however, consider reducing the apalutamide dose based on individual tolerability. Mild or moderate inhibitors of CYP2C8 or CYP3A4 are not expected to affect the exposure of apalutamide.
- Effect of apalutamide on drug metabolizing enzymes: Apalutamide is a strong inducer of CYP3A4 and CYP2C19, and a weak inducer of CYP2C9 in humans. Concomitant use of apalutamide with medications that are primarily metabolized by CYP3A4, CYP2C19, or CYP2C9 can result in lower exposure to these medications. Substitution for these medications is recommended when possible or evaluate for loss of efficacy if medication is continued. Concomitant administration of apalutamide with medications that are substrates of UGT can result in decreased exposure. Use caution if substrates of UGT must be coadministered with apalutamide and evaluate for loss of efficacy.
- Effect of apalutamide on drug transporters: Apalutamide was clinically shown to be a weak inducer of P-gp, BCRP, and OATP1B1. Concomitant use of apalutamide with medications that are substrates of P-gp, BCRP, or OATP1B1 can result in lower exposure of these medications. Use caution if substrates of P-gp, BCRP or OATP1B1 must be co-administered with apalutamide and evaluate for loss of efficacy if medication is continued.
- Corticosteroids (Oral, IV, or IM): due to possible resistance mechanisms, which may be contributed by glucocorticoid receptor signaling, concurrent use of corticosteroids during the study is not recommended; short term use (≤4 weeks) will be allowed if clinically indicated, however, its use must be tapered off as soon as possible.

The sponsor must be notified in advance (or as soon as possible thereafter) of any instances in which prohibited therapies are administered.

6.6. Dose Modification

Any dose/dosage adjustment should be overseen by medically-qualified study-site personnel (principal or sub-investigator unless an immediate safety risk appears to be present).

General principles on dose modifications (except for rash, see Section 6.6.1 for details):

- Grade 1 or Grade 2 toxicities should be managed symptomatically without dose adjustments. Appropriate medical treatment should be used.
- In the event of a Grade 3 or higher toxicity, study drug should be held as detailed in Table 3 and Table 4.

- For the first occurrence of a Grade 3 or higher toxicity, dose reductions are allowed at investigator's clinical judgment; if the Grade 3 or higher event recurs, dose reduction is mandatory.
- If Grade 3 or higher toxicity does not resolve to Grade 1 or baseline within 2 cycles, the participant should be discontinued from treatment or the investigator's rationale to continue treatment must be discussed with the sponsor.
- The investigator's rationale to re-escalate treatment must be discussed with and approved by the sponsor's medical monitor on an individual basis prior to implementation.
- Instructions for dose modifications are provided as guidance and should not replace the investigator's own clinical judgment.

Table 3 summarizes apalutamide/placebo dose modifications for drug-related toxicities (except rash). Dose modifications for drug-related rash are summarized in Table 4.

Table 3: Dose Modifications of Apalutamide/Placebo (except for rash, if rash occurs, see Table 4)

Severity	Number of apalutamide/placebo tablets
Grade 1 or 2	No change or hold until return to baseline
≥Grade 3	Hold until Grade 1 or baseline, resume at full dose; dose reductions are allowed at investigator's clinical judgment
Recurrence ≥Grade 3	Hold until Grade 1 or baseline; reduce 1 dose level; 2 dose reductions are allowed for recurrent treatment-related toxicity (180 mg [3 tablets]) and 120 mg [2 tablets]). Discontinue if toxicity persists after 2 dose reductions.
First occurrence of seizure of any grade	Discontinue
Note: Adverse events are graded according to NCI-CTCAE Version 4.03	

Abbreviation Key: NCI-CTCAE: National Cancer Institute-Common Terminology Criteria for Adverse Events.

6.6.1. Dose Modifications for Rash and Rash Management

Dose modifications for rash are allowed and are summarized in Table 4. If the skin rash has any component of desquamation, mucosal involvement, or pustules, stop dosing with study treatment, refer to a dermatologist for evaluation, and a skin biopsy is recommended (in addition to the interventions listed in Table 4) (and complete the skin rash eCRF). If the skin rash is Grade 3 or higher, asking the participant to consent to documentation by a photograph and further evaluation by a dermatologist will also be considered (and complete the skin rash eCRF). Completion of the skin rash eCRF will also be required if the skin rash leads to permanent discontinuation of study drug. If the study drug needs to be held for more than 14 days, the investigator will discuss with the sponsor's medical monitor. Apalutamide/placebo can be held up to 28 days in the event of rash. If treatment interruption for any AE grade is longer than 28 days, resumption of treatment may still be feasible. Please reach out to the sponsor to discuss further management. Dose re-escalation for rash is allowed for apalutamide/placebo at the discretion of the investigator.

Table 4: Dose-modification and Management of Drug-related Rash

Severity	Intervention
Grade 1	Continue apalutamide/placebo at current dose
	Initiate dermatological treatment ^a
	Topical steroid cream AND
	Oral Antihistamines
	Monitor for change in severity ^a
	Hold apalutamide/placebo for up to 28 days
	Initiate dermatological treatment ^a
Grade 2 (or	Topical steroid cream AND
symptomatic	o Oral Antihistamines
Grade 1) ^b	Monitor for change in severity ^a
	 If rash or related symptoms improve, reinitiate apalutamide/placebo when rash is
	Grade ≤1. Consider dose reduction at half the dose
	Hold apalutamide/placebo for up to 28 days
	Initiate dermatological treatment ^a
	Topical steroid cream AND
	Oral Antihistamines AND
G 1 sad	Consider short course of oral steroids ^c
Grade ≥3 ^d	Reassess after 2 weeks (by site staff), and if the rash is the same or has worsened, initiate
	oral steroids (if not already done) and refer the participant to a dermatologist
	 Reinitiate apalutamide/placebo at half the dose^a when rash is Grade ≤1.
	If after 28 days, rash has not resolved to Grade ≤1, contact the sponsor to discuss further
	management and possible discontinuation of study drug

Note: Rash may be graded differently according to the type of rash and associated symptoms. For example, maculo-papular rash is graded by body surface area covered and not severity of the rash. Please consult NCI-CTCAE Version 4.03 for specific grading criteria for other types of rash.

- Obtain bacterial/viral cultures if infection is suspected
- b Participant presents with other rash related symptoms such as pruritus, stinging, or burning
- If a participant previously started oral corticosteroids, continue for at least 1 week after resumption of reduced dose of apalutamide/placebo. If the proposed total oral steroid use will exceed 28 days, contact the sponsor.
- If there is blistering or mucosal involvement, stop apalutamide/placebo dosing immediately and contact the sponsor

Abbreviations: NCI-CTCAE: National Cancer Institute-Common Terminology Criteria for Adverse Events.

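### The any-grade rash stop rule in Protocol 6.6.1 does not name blistering, so asymptomatic Grade 1 blistering appears to fall under Table 4's instruction to continue study drug

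*Protocol*

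**What the plan says.** Section 6.6.1 deals with rash in text, then in Table 4, then in table footnotes.

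- **Text, second sentence of 6.6.1.** "If the skin rash has any component of desquamation, mucosal involvement, or pustules, stop dosing with study treatment". The sentence goes on to dermatology referral, a recommended biopsy and the skin rash eCRF, "in addition to the interventions listed in Table 4". It has no grade limit and does not mention blistering.
- **Table 4, Grade 1.** "Continue apalutamide/placebo at current dose", with topical steroid, antihistamine and monitoring. The row has no lesion exception and no pointer to the text.
- **Table 4, Grade 2 or symptomatic Grade 1.** "Hold apalutamide/placebo for up to 28 days". Footnote b defines the symptomatic case: "Participant presents with other rash related symptoms such as pruritus, stinging, or burning".
- **Table 4, Grade ≥3.** The same 28-day hold, with marker d on the grade label.
- **Last Table 4 footnote.** "If there is blistering or mucosal involvement, stop apalutamide/placebo dosing immediately and contact the sponsor". This is the only place where the rash section names blistering.

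The general dose-modification principles in Section 6.6 do not fill any gap, because they apply "except for rash, see Section 6.6.1 for details".

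**The concern.** The text and the footnote each list lesion features that call for stopping study drug, and the lists differ. Mucosal involvement is on both. Desquamation and pustules are only in the text, which applies at any grade. Blistering is only in the footnote, which appears to apply at Grade ≥3.

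The one Table 4 category in which dosing continues is asymptomatic Grade 1. If the footnote does not reach that row, no rash-specific instruction takes a man with asymptomatic Grade 1 blistering off study drug. The note under Table 4 says that maculo-papular rash is graded by the body surface area it covers rather than by how severe it is. A low grade therefore does not by itself rule out a worrying lesion type, and that is the situation an any-grade rule is meant to catch.

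What is at stake is participant safety in a rare situation. No efficacy analysis is involved.

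**Working it through.** No formula applies. The check sets each lesion feature against each Table 4 row.

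**Step 1: where does the blistering footnote attach?** Table 4 has four footnotes, and only b keeps its letter in the extracted text. In order they concern cultures, symptomatic Grade 1, oral corticosteroids, and blistering or mucosal involvement. Marker c sits on the oral steroid line, which matches the third footnote. Marker d sits on the Grade ≥3 label, which points to the fourth. One a marker, on the half-dose line, does not fit the cultures footnote, so the markers are not fully reliable. Attachment to Grade ≥3 is the better-supported reading, but it is an inference.

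**Step 2: feature by row, with the footnote on Grade ≥3 only.**

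| Feature | Asymptomatic Grade 1 | Grade 2 or symptomatic Grade 1 | Grade ≥3 |
|---|---|---|---|
| Desquamation | Text: stop. Table: continue | Text: stop. Table: hold | Text: stop. Table: hold |
| Pustules | Text: stop. Table: continue | Text: stop. Table: hold | Text: stop. Table: hold |
| Mucosal involvement | Text: stop. Table: continue | Text: stop. Table: hold | Text and footnote: stop |
| Blistering | Text silent. Table: **continue** | Text silent. Table: hold | Footnote: stop, contact sponsor |

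**Step 3: resolve the cells.** There are 4 features × 3 rows = 12 combinations.

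- In the three Grade 1 cells for desquamation, pustules and mucosal involvement, the any-grade text is the more specific rule and comes before a table that only summarises. The text prevails and the man stops.
- In the middle blistering cell the man is already off drug under the ordinary hold. What he lacks is immediate sponsor contact: the text asks for a medical-monitor discussion only "If the study drug needs to be held for more than 14 days".
- In asymptomatic Grade 1 blistering, nothing in the text or the table stops drug. This is the only such cell, 1 of 12.

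**Step 4: the other footnote reading.** If the footnote covers every row, that cell also becomes a stop, and 0 of 12 leave a man on drug.

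**Step 5: how many men?** Section 2.2 gives skin rash of any kind in 26% of apalutamide-treated men in the global study. If that held for all 75 participants, 0.26 × 75 = 19.5, or about 20, would have some rash. That is a ceiling on all rashes, not an estimate of this case. The documents do not give the share that blister at asymptomatic Grade 1, and it may be zero. Section 2.2 describes the rash as mostly macular or maculo-papular, with no Stevens-Johnson syndrome or toxic epidermal necrolysis.

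**The case against.** The strongest reply is that the blistering gap depends on three things the available text cannot settle.

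- The footnote's row is inferred from damaged markers, and its wording has no grade limit.
- Grading of rash other than maculo-papular is referred to NCI-CTCAE 4.03, which the documents do not reproduce, so whether a blistering rash can be Grade 1 at all is unknown here.
- Footnote b's examples are open-ended. A site could count blistering as a symptom, which leads to a hold.

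All three stand. They limit the claim to what appears to follow, but they do not remove it: even if the footnote proves general, the any-grade sentence still omits a feature that the protocol treats as a reason to stop immediately.

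The backstops also stand. Section 6.6 says the instructions do not replace clinical judgment. Section 7.1 requires discontinuation when the investigator believes safety calls for it. The Grade 1 row requires monitoring for change in severity. None of these is specific to blistering.

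A reader might infer more than this, in two ways. The first is that text and table contradict each other for desquamation, pustules and mucosal involvement. The documents do not support that. The stop sentence has no grade limit and stands above the table, Section 6.6 sends sites to Section 6.6.1, and the clause about adding to Table 4 reads naturally as adding referral and biopsy to the table's skin treatment. For these three features the defect is a missing cross-reference. The second is to count five of the twelve combinations as defective. That would include three cells that the text resolves and one in which drug is already held.

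**Conclusion.** The point holds as a minor safety-wording defect. The any-grade stop sentence omits blistering, and the only blistering stop appears to be tied to Grade ≥3. On that reading asymptomatic Grade 1 blistering stays on study drug.

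At most one of twelve feature-by-row combinations is affected, and none if the footnote covers all rows. The conclusion rests on three assumptions: the footnote belongs to Grade ≥3, a blistering rash can be graded 1, and blistering alone does not make a Grade 1 rash symptomatic. The number of men is few and possibly zero. TTPP, its analysis, power and sample size do not change. Confidence is moderate at best until the footnote placement is checked in the original PDF.

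**What to change.** Check the footnote marker in the original PDF first. Then make two wording changes:

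1. In the 6.6.1 stop sentence, add blistering to desquamation, mucosal involvement and pustules.
2. On the Table 4 Grade 1 line, after the instruction to continue, add: *unless desquamation, blistering, mucosal involvement or pustules are present (see text: stop dosing)*.

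The first change closes the gap whichever row carries the footnote. The second supplies the missing cross-reference for the other three features. Table 3 already has an any-grade line for seizure, so a grade-independent exception in a dosing table is not new to this protocol.

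The cost is a protocol amendment, with IEC/IRB approval under Appendix 2, and an occasional extra drug stop for low-grade blistering. Adding the word to the existing sentence also brings in its dermatology referral and biopsy recommendation. If the sponsor does not want those for low-grade blistering, a separate clause that only stops dosing is enough. New sponsor contact for desquamation or pustules is not needed to close this gap. No visit or data collection is added, as the skin rash eCRF already exists.

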6.7. Long-term Follow-up

Investigators will recontact the participant to obtain posttreatment follow-up information regarding the participant's safety or survival status as noted in the informed consent form (refer to Informed Consent in Appendix 2: Regulatory, Ethical, and Study Oversight Considerations).

Participants will be instructed that study intervention will not be made available to them after they have completed/discontinued study intervention and that they should return to their primary physician to determine standard of care.

7. DISCONTINUATION OF STUDY INTERVENTION AND PARTICIPANT DISCONTINUATION/WITHDRAWAL

7.1. Discontinuation of Study Intervention

Discontinuing treatment will not result in an automatic withdrawal from the study. Participants who discontinue treatment, but do not withdraw consent, should complete the EoT Visit within 30 days of the last dose of study drug and continue the scheduled assessments according to the Posttreatment Follow-up Phase in the Schedule of Activities (SoA).

A participant's study intervention must be discontinued if:

- Documented distant metastases
- The investigator believes that for safety reasons or tolerability reasons (eg, AE) it is in the best interest of the participant to discontinue study intervention
- Initiation of any subsequent prostate anticancer therapy or procedure not specified in the protocol during treatment phases
- Seizure of any grade or Grade 4 neurotoxicity (see Section 6.6);
- Other study drug toxicity (see Section 6.6)
- Withdrawal of consent for continued treatment.

All participants discontinuing study treatment will enter the Posttreatment Follow-up Phase. For participants entering Posttreatment Follow-up Phase with evidence of distant metastasis, they will be followed for survival status, the development of symptomatic progression, initiation of any new systemic anticancer therapies until death, withdrawal of consent for study participation, or termination of the study (every 4 months ± 7 days via clinic visit, telephone contact or an alternative contact method per institution policy/practice), whichever comes first. In addition, if participants discontinued study treatment prior to documented disease progression (distant metastases), CT of the chest, abdomen, and pelvis, or MRI, plus bone scan will be obtained and evaluated for disease progression in Posttreatment Follow-up visits (every 16 weeks ± 7 days), until documentation of disease progression, then participants will be contacted every 4 months (± 7 days) to obtain survival status, recording of development of symptomatic progression, initiation of any new systemic anticancer therapies until death, withdrawal of consent for study participation, or termination of the study.

When a participant withdraws before completing the study, the reason for withdrawal is to be documented in the eCRF and in the source document. Study drug assigned to the withdrawn participant may not be assigned to another participant. Participants who withdraw will not be replaced.

Participants will be followed for at least 30 days after the last dose of study drug. If a participant is withdrawn from treatment due to an AE, please refer to Appendix 3: Adverse Events: Definitions and Procedures for Recording, Evaluating, Follow-up, and Reporting.

